4.2 Assessment of Exclusion Criteria

The exclusion criteria related to laboratory assessments:

- Has known active hepatitis A immunoglobulin M, hepatitis B surface antigen, or hepatitis C antibody;
- Is human immunodeficiency virus positive;
- Has creatinine clearance <15 mL/min or is on any form of dialysis

will be assessed from patient history when the last assessment of these criteria occurred not more than or equal to 180 days before Visit 1.

If the last assessment occurred more than 180 days ago, laboratory assessments for these criteria will be performed on V0. Patients will be instructed to either represent for V1 or, when V0 and V1 are held on the same day, to initiate study drug when the laboratory results are available and the patient eligibility has been confirmed. In the latter cases, eligibility will be communicated to the patient by telephone call.

Laboratory assessments of these criteria, and a serum pregnancy test (if applicable), will be performed as confirmation at Visit 1 in all cases.

4.3 Withdrawal of Patients From the Study

The duration of the study is defined for each patient as the date signed written informed consent is provided through the last follow-up visit 6 months after PEA. The approximate study duration is 1 year for each patient including a screening period of 3 months, double-blind treatment period of 3 months, and a safety follow-up period of 6 months.

4.3.1 Reasons for Withdrawal/Discontinuation

Patients may withdraw from the study at any time and for any reason without prejudice to their future medical care by the investigator or at the study site. Every effort should be made to keep patients in the study. The reasons for patients not completing the study will be recorded. A patient may be withdrawn from the study for any of the following reasons:

1. Does not meet the protocol inclusion or exclusion criteria
2. Noncompliance with the protocol
3. A serious or intolerable AE that in the investigator's opinion requires withdrawal from the study
4. Laboratory safety assessments that reveal clinically significant haematological or biochemical changes from the baseline values
5. Symptoms or an intercurrent illness not consistent with the protocol requirements or that justifies withdrawal
6. Loss to follow-up
7. Other (eg, pregnancy, development of contraindications of use of study drug)
8. If the investigator believes that continued administration of the study drug is contrary to the best interests of the patient
9. The patient withdraws consent or the investigator or sponsor decides to discontinue the patient's participation in the study

The investigator will also withdraw a patient if International CTEPH Association (ICA) terminates the study. Upon occurrence of a serious or intolerable AE, the investigator will confer with the sponsor. If a patient is discontinued because of an AE, the event will be followed until it is resolved. Any patient may withdraw his or her consent at any time.

4.3.2 Handling of Withdrawals

Patients are free to withdraw from the study or study drug at any time upon request. Patient participation in the study may be stopped at any time at the discretion of the investigator or at the request of the sponsor.

Patients who discontinue study drug or active participation in the study will no longer receive study drug. When a patient withdraws from the study, the reason(s) for withdrawal shall be recorded by the investigator on the relevant page of the electronic case report form (eCRF). Whenever possible, all patients who discontinue study drug or withdraw from the study prematurely will undergo 6-month safety follow-up visit (Visit 4) assessments. Patients who fail to return for final assessments will be contacted by the site in an attempt to have them comply with the protocol.

It is vital to obtain follow-up data on any patient withdrawn because of an AE or SAE. In every case, efforts must be made to undertake protocol-specified, safety follow-up procedures.

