Based on the quality of the RHC data and the experience of the referring site, a referred patient (a patient where the previous RHC was performed at a site other than the study site) can be enrolled in the study based on investigator's discretion. The data of haemodynamic parameters at screening will be collected from the previous RHC.

Patients who permanently discontinue study drug for any reason (ie, due to meeting the protocol-mandated safety monitoring criteria) or who withdraw from the study prematurely (prior to the end of the double-blind treatment period) will participate in the end-of-study safety follow-up visit.

Efficacy and safety assessments will be performed throughout the study, as presented in the schedule of events (Table 12-1). The primary efficacy measure is the reduction in PVR.

Additional efficacy measures include cardiac index, mean right atrial pressure (mRAP), mPAP, pulmonary artery wedge pressure (PAWP), number and cause of deaths during the study, PH-related hospitalisation, need for PAH-targeted and other medications, change in WHO functional class for PAH, perioperative findings that include circulatory arrest time and surgery-related complications, surgical evaluation of specimen, withdrawal during the treatment phase, NT-proBNP concentration, length of hospital and intensive care unit (ICU) stay, and time on mechanical ventilation.

Safety assessments include monitoring of AEs, vital sign measurements, electrocardiogram (ECG) measurements, physical examinations, clinical laboratory examinations, and pregnancy testing.

The end of the study is defined as when the last patient completes the last visit of the study ie, 6-month follow-up visit (Visit 4).

An unblinded, independent data safety monitoring board will periodically review safety data and other study information during the conduct of the study.

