- When frequency counts are presented, the percentage will be suppressed when the count is zero in order to draw attention to the non-zero counts. A row denoted “Missing” will be included in count tabulations where specified on the shells to account for dropouts and missing values. Percentages will be based on the total number of patients in the respective analysis set unless otherwise specified.
- Unless otherwise specified, statistical tests will be 2-sided and performed using a 5% significance level, leading to 95% (2 sided) confidence intervals (CIs). Modelling techniques will be used in an exploratory sense. No adjustments for multiplicity are made.
- Partial dates will be imputed based on the rules specified in Appendix 13.4.
- All laboratory data will be reported by using the International System of Units.
- Unless otherwise specified, the baseline will be defined as the last valid assessment, including assessments from the unscheduled visit, prior to the study drug administration.
- A Visit 2 assessment is considered as valid only when the assessment is completed within 7 days prior to PEA. For assessments at Visit 4, the nominal visit collected in electronic case report form (eCRF) will be used in the analysis. This rule is applicable to all endpoints derived by the visit.
- By-patient listings will be created for each eCRF module for all screened patients. Patients will be identified in the listings by patient number. If data are to be summarised by visit, the visit name collected on the eCRF page will be used.
- All analyses will be conducted using SAS® software Version 9.3 or later (SAS Institute Inc, Cary, North Carolina).

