7.2.2. Treatment Compliance

Patient compliance with study drug will be assessed by the investigator and/or study personnel at Visit 2 and during a telephone call using direct questioning and tablet counts. Deviations from the prescribed treatment regimen will be recorded on the source document and the patient's eCRF.

The overall treatment compliance (%) will be evaluated by calculating the number of tablets taken by the patient divided by the number of tablets expected to be used during the treatment period and multiplied by 100.

The number of tablets taken will be calculated by subtracting the number of tablets returned from the number of tablets dispensed. The number of tablets expected will be calculated by multiplying the total number of days of planned exposure to study drug (treatment duration) by the number of tablets planned per day (3 tablets per day).

The overall treatment compliance (%) will be summarised using descriptive statistics.

A patient is considered compliant if overall treatment compliance is greater than or equal to 80%. A categorical summary of whether patients were compliant (yes/no) will be present. The number and percentage of patients in compliance category of <80%, >=80 and <=120%, and >120% will also be presented.

By-patient listing will be provided to support the summary table.

8. Efficacy Analysis

The primary analysis will use ITT set, all analyses on perioperative endpoints will use PEA set only; all analyses on postoperative endpoints will use PEA set and PPS. For other endpoints, the analysis set to be used is specified in each subsection below. By-patient listings will be provided to support the summary tables.

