8.2.1. Pulmonary Vascular Resistance (PVR)

The difference in the percent change from baseline in PVR at Visit 4 between riociguat and placebo will be tested using the 2-sample Wilcoxon rank-sum test for the PEA set and the PPS.

PVR assessment at Visit 4 will use the nominal visit information collected in eCRF without considering the time window because PVR status is expected to be stable after PEA.

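### A value labelled Visit 4 can be analysed as a 6-month post-PEA result although nothing requires it to follow PEA or to fall near 6 months

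*Protocol*

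**What the plan says.** **Who has Visit 4 assessments.** Protocol 4.3.2 says, with the qualifier that this applies where possible, that "all patients who discontinue study drug or withdraw from the study prematurely will undergo 6-month safety follow-up visit (Visit 4) assessments". No timing is attached. Protocol 3.1 says that patients who stop drug permanently, or withdraw before the double-blind period ends, "will participate in the end-of-study safety follow-up visit". The Schedule of Events (Protocol Table 12-1, SAP 13.1) runs from Visit 0 to Visit 4, places Visit 4 at Day 276±10, and has no early-termination visit.

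**How Visit 4 is analysed.** For PVR, SAP 8.2.1 states: "PVR assessment at Visit 4 will use the nominal visit information collected in eCRF without considering the time window". Protocol 7.2 has the same rule. SAP 4 generalises it: "For assessments at Visit 4, the nominal visit collected in electronic case report form (eCRF) will be used in the analysis", and then "This rule is applicable to all endpoints derived by the visit". Protocol 7.3 does likewise.

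**How Visit 2 is treated.** SAP 4 is strict here: "A Visit 2 assessment is considered as valid only when the assessment is completed within 7 days prior to PEA".

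**Which patients count.** The opening of SAP 8 says that "all analyses on postoperative endpoints will use PEA set and PPS". SAP 4.3.2 defines the PEA set as the ITT patients who had the operation.

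**The concern.** The Visit 4 endpoints are meant to describe the patient 6 months after surgery. The plan checks that a Visit 2 value sits correctly relative to PEA, but has no matching check for Visit 4. The schedule's ±10 day window plays no part in the analysis.

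The reason given is that PVR may be taken "without considering the time window because PVR status is expected to be stable after PEA". That cannot justify a value taken before PEA. It also says nothing about NT-proBNP, functional class or the other haemodynamic measures, to which SAP 4 extends the rule.

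If stopping drug or leaving the study differs between arms, a difference in when Visit 4 was done could appear as a difference in 6-month outcome, or could mask one. Because all the values would carry the same label, the tables would not show it.

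**Working it through.** **1. Who could contribute an off-time value?** Applying the rules as written:

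- *Stops or withdraws and never has PEA.* Outside the PEA set and the PPS, so absent from the formal postoperative endpoints. One place is left open: the by-visit PVR table and boxplot in SAP 8.1 include Visit 4 and name no analysis set. SAP 8.1 uses ITT for the primary analysis, while the opening of SAP 8 and item 2 of SAP 11 point to the PEA set and PPS for Visit 4 PVR.
- *Stops drug before surgery, has the Visit 4 assessments then, and later has PEA.* In the PEA set, with an unoperated value labelled Visit 4. No rule removes it. The PPS may not remove it either: SAP 7.2.2 bases expected tablets on treatment duration, which SAP 7.2.1 counts from first to last dose, so on that reading an early stopper can still reach 80% compliance.
- *Has PEA, leaves the study soon after, and has the assessments on leaving.* In the PEA set, with an early postoperative value. If PVR is stable after PEA, its PVR is little affected. The stated reason does not cover NT-proBNP, functional class or the other haemodynamics.
- *Stops drug, stays in the study, and attends at the planned time.* The value is correct.

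**2. The plan's own figures.**

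- Sample size (Protocol 4.3.3): 80 completers with 10% dropout. 80 × 1.10 = 88, which matches; 80 / 0.90 = 88.9, or 89. Planned dropouts are 88 − 80 = 8.
- Visit 4 timing: Day 96 + 180 = Day 276. The scheduled window is Day 266 to 286, that is 266 − 96 = 170 to 286 − 96 = 190 days after the Day 96 visit. The analysis rule accepts any day.

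**3. Illustration for PVR.** The documents give neither the number of affected patients nor the expected 6-month change, so the following are assumptions:

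- true 6-month change of −40% to −75%;
- pre-PEA value, expressed as change from baseline, of 0% to −28%. The −28% is 226/800 = 28.25%: the PVR decrease on riociguat in the pivotal CTEPH trial (Protocol 3.1.1) over the entry threshold;
- n = 88/2 = 44 per arm, with *m* affected values, all in one arm.

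Shift in that arm's mean = (*m*/n) × (pre-PEA value − true 6-month value):

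| *m* | Smallest shift | Largest shift |
|---|---|---|
| 1 | 1/44 × (−28 + 40) = 0.3 | 1/44 × (0 + 75) = 1.7 |
| 4 | 4/44 × (−28 + 40) = 1.1 | 4/44 × (0 + 75) = 6.8 |

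The units are percentage points. They apply to the descriptive means in SAP 8.1.

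**4. Rank-based analyses.** SAP 8.2.1 tests Visit 4 PVR with the Wilcoxon rank-sum test, and SAP 8.3 uses Hodges-Lehmann estimates for the exploratory measures. With 44 per arm, four values at 0% where −60% is true, and an assumed SD of 10 to 25 points, simulation gives a Hodges-Lehmann shift of roughly 2 to 4 points. The mean shifts by 4/44 × 60 = 5.5.

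**The case against.** The strongest reply is that the timing problem is not in the text. Protocol 4.3.2 names the visit by its 6-month timing, Protocol 3.1 calls it an end-of-study visit, and Protocol 4.3 runs each patient's study to 6 months after PEA. Read that way, patients who stop early are simply followed to the planned visit. This reading is fair, and it means that early values *can* enter, not that they do. It fits less well for someone leaving the study, and it cannot work for a patient who never has PEA and so has no 6-month date. Sites could act differently on the same sentence.

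Other parts of the reply stand:

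- The pre-PEA case needs several things to coincide: an early catheterisation, a Visit 4 label, a later PEA, and no proper Visit 4 value afterwards that replaces it. Nothing in the documents says how often this would happen.
- The composite rests on death, hospitalisation and therapy events and on the worst functional class after treatment (SAP 8.2.2), so it depends little on the Visit 4 label.
- NT-proBNP, the other haemodynamics and functional class by visit are exploratory and not formally tested (SAP 8.3).
- Study drug ends at PEA, so intolerance of it could prompt stopping before surgery but not leaving afterwards.
- A strict window as the main rule would also discard late but valid values. It is better used as a sensitivity analysis.

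What the reply does not answer is that neither document requires a Visit 4 value to follow PEA or says how a brought-forward assessment is labelled, and that the stable-PVR reason covers neither pre-PEA values nor other measures.

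**Conclusion.** The gap is real and should be closed before database lock. Followed literally, the rule would analyse a pre-PEA or just-post-PEA value as a 6-month result for PVR, the other haemodynamics, NT-proBNP and functional class at Visit 4.

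The size of any bias cannot be derived from the documents. The 0.3 to 6.8 points for 1 to 4 pre-PEA values in one arm of 44 rest on assumed changes and a one-sided split, and the upper end is an extreme case. Rank-based results are likely to move less. Values taken after PEA would move PVR little if it is stable, as the plan assumes.

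A reader might infer three stronger things that the documents do not support:

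- *That never-operated dropouts distort the 6-month comparison.* The PEA set and PPS keep them out of the formal endpoints.
- *That the 10% dropout assumption gives the number of contaminated values.* Protocol 4.3.3 counts as dropouts those who leave before Visit 4, so they are not among the 80 completers. Patients who only stop drug are not counted in that figure.
- *That early values are systematically worse.* For PVR soon after surgery, nothing in the plan says so.

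**What to change.** - **SAP 4 and 8.2.1:** count a Visit 4 value towards the 6-month endpoints only if it is dated after the patient's own PEA and is not an assessment brought forward because of premature withdrawal. Record this in SAP 11, because Protocol 7.2 and 7.3 carry the same unrestricted rule.
- **Visit mapping:** give brought-forward assessments a separate early-termination label, used for safety summaries and listings.
- **Sensitivity analysis:** repeat the Visit 4 analyses using only values within a stated window around 6 months after PEA.
- **SAP 8.1:** name the PEA set for Visit 4 in the by-visit PVR table and boxplot.
- **Protocol 4.3.2:** state when patients who stop drug but stay in the study have Visit 4.

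The cost is a few sentences and one mapping rule in programming. PEA dates are already needed for the 7-day Visit 2 rule, and visit dates for censoring in SAP 8.2.5. The sample size does not change. The downside is a few fewer Visit 4 values.

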4.3.3 Replacements

A total of 88 patients will be randomly assigned in the study with a target of 80 patients completing the study with an assumption of a 10% dropout rate.

Therefore, drop out for any reason before the last follow-up visit (Visit 4) will be monitored continuously throughout the study, and patients that drop out will be replaced to make a total number of 88 randomised patients. In case of a high initial dropout rate, the DSMB and the sponsor will evaluate the reasons for drop out and decide in mutual agreement on potential extension of further randomisations.

5 Study Drugs

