5.6 Blinding

The clinical study will be performed in a double-blinded manner. The investigator, study coordinator(s), patients, and the sponsor study team and its representatives will be blinded to the identity of the randomised treatment assignment from the time of randomisation until database lock. Randomisation data will be kept in strict confidence by the statistician who will generate the randomisation schedule, the IWRS provider, and the vendor involved in the study drug labelling. The identity of the treatments will be concealed by the use of study drugs that are all identical in packaging, labelling, schedule of administration, appearance, taste, and odour.

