6.5 Safety Monitoring Committee

An unblinded, independent DSMB will periodically review safety data. The frequency of data review and DSMB processes are outlined in the DSMB charter. In brief, the DSMB will meet before study start, after approximately 8 subjects have completed at least 12 weeks of study drug treatment and undergone PEA, after approximately 20 subjects have completed at least 12 weeks of study drug treatment and undergone PEA and after approximately 20 subjects have completed the study. An optional meeting is scheduled after 30–40 patients have completed the study. The DSMB will periodically review unblinded study information during the conduct of the study. If necessary, unblinding of individual patient data and treatment groups may be done.

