7.5 Sample Size Calculations

A total of 88 patients, accounting for a 10% dropout rate, will be randomly assigned into riociguat or placebo groups at a ratio of 1:1 in the study. The sample size for this study is not based on the required statistical power to test any specific hypothesis but feasibility to initially assess the safety and efficacy of riociguat on preoperative pulmonary haemodynamics in patients with operable CTEPH.

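### Any extension of randomisation is agreed between the unblinded DSMB and the blinded sponsor on dropout reasons; it should rest with the sponsor on pooled, blinded data

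*Protocol*

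**What the plan says.** **Size and replacement.** Protocol 4.3.3 states "A total of 88 patients will be randomly assigned in the study with a target of 80 patients completing the study"; the dropout rate it assumes is 10%. Protocol 7.5 gives the same total, "A total of 88 patients, accounting for a 10% dropout rate", and SAP 4.1 repeats it. Protocol 4.3.3 goes on to say that "drop out for any reason before the last follow-up visit (Visit 4) will be monitored continuously throughout the study" and that "patients that drop out will be replaced to make a total number of 88 randomised patients".

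**Extension.** If early dropout is high, Protocol 4.3.3 provides that "the DSMB and the sponsor will evaluate the reasons for drop out and decide in mutual agreement on potential extension of further randomisations". It gives no dropout rate that counts as high and no maximum number of patients.

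**Who knows what.** Protocol 6.5: "An unblinded, independent DSMB will periodically review safety data". The same section says the board sees unblinded study information, and Protocol 3.1 extends its review beyond safety data to other study information. On the other side, Protocol 5.6 says that "the sponsor study team and its representatives will be blinded to the identity of the randomised treatment assignment", from randomisation to database lock.

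**Elsewhere.** Protocol 7.8.5 and SAP 10 describe the board as reviewing safety data and making recommendations, and refer to the charter for detail. The SAP has no rule on replacement or extension.

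**The concern.** Two parties on opposite sides of the blind are asked to make one decision together, and the material for that decision is why patients left the study. In this trial those reasons are close to the outcomes. Deaths and withdrawals before PEA are secondary endpoints, and a patient who does not reach PEA also has no primary endpoint value.

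Two things are at stake. First, the final number randomised could depend partly on information by arm, which is a source of operational bias even when nobody intends it. Second, a board that knows the arms has to argue for or against an extension with a sponsor that must not know them. The position it takes, or the reasons it stresses, can convey something about the arms.

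**Working it through.** **1. Reproduce the 88.** Inputs from Protocol 4.3.3: 80 completers, 10% dropout.
- Multiplying up: 80 × (1 + 0.10) = 88, the plan's figure.
- Dividing: 80 / (1 − 0.10) = 88.9, rounded up to 89.
- Check: 88 × 0.90 = 79.2 expected completers; (88 − 80) / 88 = 9.1% dropout leaves exactly 80.

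The figure reproduces to within one patient, and the dropout allowance is inside it.

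**2. Read the replacement sentence against that figure.** A patient who drops out after randomisation is already one of the 88, so the sentence is awkward. It becomes coherent if the 8 patients above 80 are themselves the replacements: 80 + 8 = 88. On that reading 88 is the routine ceiling, in line with Protocol 7.5 and SAP 4.1. It also explains why a separate clause is needed to go beyond 88.

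**3. Set the extension clause beside the blinding sections.**

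| Question | Where | Answer |
|---|---|---|
| Who decides on extension? | Protocol 4.3.3 | DSMB and sponsor, by agreement |
| On what? | Protocol 4.3.3 | Reasons for dropout |
| Does the DSMB know the arms? | Protocol 6.5 | Yes |
| May the sponsor team know them? | Protocol 5.6 | No, until database lock |
| What is the DSMB's role elsewhere? | Protocol 7.8.5, SAP 10 | Safety review and recommendations |
| Trigger, maximum, pooled data only? | Protocol, SAP | Not stated |

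In Protocol 4.3.3 the board shares a sample-size decision; in 7.8.5 and SAP 10 it recommends on safety.

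**4. Do dropout reasons carry information on outcome?** Protocol 7.2 lists all-cause death and withdrawal during the randomised phase as secondary endpoints. SAP 5.1 lists adverse event, death and progressive disease among the recorded reasons for not completing. Protocol 7.1 treats Visit 2 PVR as missing when PEA is not done. Seen by arm, such data are outcome data.

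**5. Why the trigger needs a number.** Take 88 randomised and independent dropout at rate d. The chance of at least 80 completers is the binomial tail P(X ≥ 80), with X ~ Bin(88, 1 − d):

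| d | P(at least 80 of 88) | N for 80 completers, 80/(1 − d) |
|---|---|---|
| 10% (plan) | 47.7% | 88.9, so 89 |
| 15% (assumed) | 7.4% | 94.1, so 95 |
| 20% (assumed) | 0.5% | 100 |

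Even at the planned rate, the chance of falling short of 80 is 100 − 47.7 = 52.3%. A small shortfall is therefore no evidence that dropout is high, and without a stated threshold the decision is left to judgement.

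**The case against.** The best defence has four parts.

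- **The trigger is not efficacy.** The clause is opened by early dropout, and nothing says that the board reviews PVR by arm. This stands. A reader might infer inflated type I error. A worst-case simulation (test at 79 completers, stop if significant, otherwise extend to 88, 97 or 106 and test again without adjustment) gives about 6.5%, 7.0% or 7.4% instead of 5%. That assumes an extension driven by PVR results, a mechanism the protocol does not describe, so these figures do not measure this problem.
- **No text passes arm-level data to the sponsor.** The sponsor already has access to dropout reasons in blinded form: they go into the eCRF (Protocol 4.3.2), and investigators confer with it on serious or intolerable events (4.3.1). Pooled reasons would add nothing about arms. This stands as far as it goes, but the clause does not limit the discussion to pooled data, and one party to it knows the arms.
- **The charter may hold a firewall.** It may, and so the leak is a risk and not a documented defect. A charter rule would still leave Protocol 4.3.3 assigning the decision to both parties.
- **The trial is exploratory, with a size set by feasibility.** No power statement is undermined. A null hypothesis is nevertheless tested at the two-sided 5% level (Protocol 7.8 and 7.8.1), and the double blind is a central claim of the design.

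A reader might also infer that replacement cannot be carried out, or that it allows about 98 patients (88 / 0.9 = 97.8). The documents do not support either. The 98 takes 88 as the completion target, whereas Protocol 4.3.3 names 80, and the 80 + 8 reading is coherent.

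**Conclusion.** The point holds as a matter of who decides an extension and on what data. Protocol 4.3.3 gives an unblinded board and a blinded sponsor a joint decision on sample size, based on reasons that overlap with secondary endpoints. The visible text sets no threshold, no maximum and no restriction to pooled data. Influence of arm-level information on the final size, and exposure of the sponsor's blind, are therefore possible as written; neither is shown to occur.

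No bias can be calculated. The conclusion rests on the protocol and SAP alone and could soften if the charter separates the two parties. The replacement sentence is ambiguous and needs tidying, but the 88 stands. This is a cheap improvement and does not undermine the planned analysis.

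**What to change.** In Protocol 4.3.3:

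1. State that 88 is the total randomised, that it includes the 10% allowance for 80 completers, and that there is no further routine replacement.
2. State that any extension is decided by the blinded sponsor from dropout counts and reasons pooled over arms.
3. Give a numerical dropout trigger and a maximum number randomised. The last column of the second table above shows what the 80-completer target implies at assumed rates; the choice is the sponsor's.
4. Limit the DSMB to one-way safety recommendations, as Protocol 7.8.5 already describes, with no discussion of dropout by arm with the sponsor.

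Repeat the rule in the SAP, which is silent on it, and in the charter.

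The cost is an amendment to wording in three documents, and the sponsor loses some flexibility to extend by negotiation. The board can still raise a safety concern about dropout at any time.
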